Visit Window ^a	Day 1	Day 29 to Day 43
Informed consent/assent	X	
Demographics	X	
Medical history	X	
Smoking status	X	
Prior/concomitant vaccination and/or immunosuppressive drugs, including systemic corticosteroids, immune-modifying drugs, or monoclonal antibodies	X	X
Physical examination	X	
Prevaccination axillary temperature	X	
Urine pregnancy test ^b	X	
Inclusion and exclusion criteria	X	
Temporary delay criteria	X	
Immunogenicity blood sampling	X ^c	X
Investigational product administration	X	
30-Minute postvaccination observation and assessment of acute reactions	X	
Train subject or a legally acceptable representative/parent/legal guardian to use e-diary and set up e-diary for the subject	X	
Dispense e-diary, digital thermometer, and caliper	X	
Subjects to record local reactions and systemic events in e-diary	6- to <18-year age group: Day 1 to Day 7 18- to <65-year age group: Day 1 to Day 14	
Review e-diary data ^d	X-----X	
Collect e-diary		X
Serious and nonserious adverse event collection	X-----X	

Abbreviation: e-diary = electronic diary.

- a. Day relative to study vaccination (Day 1).
- b. For female subjects of childbearing potential. Pregnancy tests will also be done whenever 1 menstrual cycle is missed during the active treatment period (28 days after vaccination) (or when potential pregnancy is otherwise suspected).
- c. Immunogenicity blood sampling at Day 1 must occur before administration of investigational product.
- d. Investigators (or appropriately qualified designees) review the e-diary data online at frequent intervals after Day 1.

090177e190dcce76Approved\Approved On: 06-May-2019 11:21 (GMT)

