6.2. Visit 2-Follow-up Visit (28 to 42 Days After Visit 1)

- Collect the subject's e-diary.
- Review the subject's e-diary and follow up on any ongoing symptoms. Record their stop date or confirm that they are still continuing on the CRF.
- Obtain and record AEs and SAEs as described in Section 8 and the Schedule of Activities.
- Obtain and record any nonstudy vaccinations, and/or immunosuppressive drugs, including systemic corticosteroid, immune-modifying drugs, or monoclonal antibodies, received since the last study visit.
- Collect a blood sample (approximately 10 mL) for immunogenicity assessments and record sample tracking information on the CRF.
- Complete the source documents and the CRF.

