**Other Reporting Summaries:**

➤ Subjects Reporting the Specific Reaction or Any Local Reaction on Each Day

The number of subjects reporting “yes” for at least 1 day or “no” for all days (these values are used as the denominators for the percentage calculations), number of subjects reporting at least 1 occurrence of the specified reaction or any reaction for that day (and any day), and observed proportion of subjects.

The above is repeated for moderate or severe reactions.

➤ Duration (Days) of Local Reactions

The number of subjects reporting “yes” for at least 1 day or “no” for all days, number of subjects reporting the specified reaction, mean, range (minimum, maximum), standard deviation, and number of unknown durations.

090177e190dce77Approved\Approved On: 06-May-2019 11:24 (GMT)

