### **Analysis Specifications**

The number of subjects reporting the specified reaction, mean, range (minimum, maximum), and standard deviation will be calculated from the number of subjects reporting the specified reaction.

The duration of the specified reaction will be calculated as the number of days from the start of the first reported reaction to the resolution of the last reported reaction, inclusive. Resolution is the last day on which the reaction is recorded in the e-diary if the reaction lasted 7 days (6- to <18-year age group) or 14 days (18- to <65-year age group) or less, or the date on which the reaction ended if it continued beyond Day 7 or 14 (the latter will be collected on the CRF). If there is no known date when the reaction ended, then duration will be missing (unknown). Subjects with no reported reaction have no duration because it is not applicable.

➤ Duration (Total Days) of Local Reactions

The number of subjects reporting “yes” for at least 1 day or “no” for all days, number of subjects reporting the specified reaction, mean, range (minimum, maximum), standard deviation, and number of unknown durations.

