### **Analysis Specifications**

The number of subjects reporting the specified reaction, mean, range (minimum, maximum), and standard deviation will be calculated from the number of subjects reporting the specified reaction.

The total days will be calculated as the sum total of reported days of the specified reaction. However, if the reaction continues beyond Day 7 or 14, the calculation of total days will include all days from the last e-diary day until the date of resolution collected on the CRF. If there is no known date when the reaction ended, then duration beyond Day 7 or 14 will be missing (unknown). Subjects with no reported reaction have no duration because it is not applicable.

➤ Summary of Day of Onset of Local Reactions

The number of subjects reporting the specified reaction or any reaction, mean, range (minimum, maximum), and standard deviation.

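### In the Duration (Days) table, a reaction confirmed as still continuing at Visit 2 is set to missing, so it leaves the mean, SD and range because it is long

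*SAP*

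**What the plan says.** SAP 6.1.1.1 lists two duration tables under its other reporting summaries: Duration (Days) and Duration (Total Days). SAP 6.1.1.2 applies the same rules to systemic events.

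- **Duration (Days).** Duration runs from the first reported day of the reaction to the resolution of the last reported one, inclusive. The end comes from the e-diary or, for a reaction that outlasts the diary period, from the CRF. Where no end date exists, "If there is no known date when the reaction ended, then duration will be missing (unknown"). The table prints the mean, the range, "standard deviation, and number of unknown durations". The specification adds that the mean, range and "standard deviation will be calculated from the number of subjects reporting the specified reaction".
- **Duration (Total Days).** This is the sum of days on which the reaction was reported, and "if the reaction continues beyond Day 7 or 14, the calculation of total days will include all days from the last e-diary day" up to the CRF resolution date. If no end date is known, only the part beyond Day 7 or 14 is called missing. This table also prints "mean, range (minimum, maximum), standard deviation, and number of unknown durations".
- **Data collected.** For symptoms still ongoing, Protocol 6.2 instructs the site at Visit 2 to "Record their stop date or confirm that they are still continuing on the CRF". The Schedule of Activities places Visit 2 at "Day 29 to Day 43". The diary runs to Day 7 for ages 6 to <18 years and to Day 14 for ages 18 to <65 years.

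**The concern.** The protocol produces two different states at Visit 2: ended on a known date, or confirmed as continuing. The SAP has a rule only for the first. The second falls under the missing-date rule, although it is right-censored with a known lower bound. The value is lost because the reaction is long, so the missingness depends on the quantity being summarised.

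If any reaction is in that state, the Duration (Days) mean can be too short. The printed maximum can also lie below a duration that the CRF already shows was exceeded. The count of unknown durations does not repair this, because it gives no lower bound. It also merges known-long reactions with those whose stop date was not obtained, which may have been short.

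The stakes are limited to how the duration of reactogenicity is described. In a descriptive study whose primary objective is safety and tolerability, with about 50 subjects in the younger group, one omitted reaction could visibly alter that description.

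**Working it through.** The documents give no duration figure to reproduce, so the check starts from the visit and diary windows.

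**Inputs from the documents.** Visit 2 is on Day 29 to 43. Onset within the diary is Day 1 to 7 (6 to <18 years) or Day 1 to 14 (18 to <65 years).

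**Step 1: minimum for Duration (Days).** For a reaction continuing at Visit 2, L = Visit 2 day − onset day + 1. Symptom-free gaps do not lower L, because this table counts from first report to final resolution.

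| Group | Visit Day 29, latest onset | Visit Day 29, onset Day 1 | Visit Day 43, latest onset | Visit Day 43, onset Day 1 |
|---|---|---|---|---|
| 18 to <65 years | 29 − 14 + 1 = 16 | 29 − 1 + 1 = 29 | 43 − 14 + 1 = 30 | 43 − 1 + 1 = 43 |
| 6 to <18 years | 29 − 7 + 1 = 23 | 29 − 1 + 1 = 29 | 43 − 7 + 1 = 37 | 43 − 1 + 1 = 43 |

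**Step 2: shift in the mean.** The documents do not say how many reactions will continue, so the effect is given per 1% of reactors. With m the mean of the known durations, the true mean exceeds the tabulated mean by at least 0.01 × (L − m), for a Day 29 visit:

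- m = 3 days (assumed): L = 16 gives 0.13 day, L = 23 gives 0.20 day, L = 29 gives 0.26 day.
- m from 2 to 5 days (assumed range): L = 16 gives 0.14 down to 0.11 day, and L = 23 gives 0.21 down to 0.18 day.

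**Step 3: illustrative counts.** With n reactors, k continuing and a known mean of 3 days, the mean is at least ((n − k) × 3 + k × L) / n. The reactor counts are assumed.

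- Adults, 1 of 60 (1.7%): (59 × 3 + 16) / 60 = 3.22, or (59 × 3 + 29) / 60 = 3.43, instead of 3.0.
- 6 to <18 years, 1 of 20 (5%): (19 × 3 + 23) / 20 = 4.00, or (19 × 3 + 29) / 20 = 4.30, instead of 3.0.
- k = 0: 3.00, no change.

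If the known durations also have SD 2 (assumed), entering the single continuing reaction at 29 days moves the SD from 2.0 to 3.9 in the adult example and to 6.1 in the younger one.

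**Step 4: Duration (Total Days).** The onset-day formula does not apply here, because symptom-free days are not counted. The minimum is the reported days before the last e-diary day, plus all days from that day to Visit 2. Take an adult who reports the reaction on Days 1 and 14 only and is still continuing on Day 29. The minimum is 1 + (29 − 14 + 1) = 17 days, whereas the Step 1 formula would give 29. The SAP text leaves two readings: the subject's total is unknown, or it stops at the last diary day (2 days here). Either way the tabulated duration is understated.

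**Step 5: base of the mean.** A missing duration has no value to contribute. For Duration (Days), the actual base is therefore reporters minus unknown durations, not all reporters as stated.

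**The case against.** The loss is disclosed. Both tables print the number of subjects reporting the reaction and the number of unknown durations, so a reader can derive the base of the Duration (Days) mean by subtraction. The statement about the base is loose wording, not a concealed denominator. Duration is not an endpoint; the primary endpoints are the number, proportion and severity of reactions. Every effect size above rests on an assumed mean and an assumed number continuing, and there may be none. Fever is least exposed, because Protocol 7.2.1.5 has temperature collected daily until it resolves. All of this stands, and it keeps the priority low. It does not remove the defect: the CRF separates a confirmed-continuing reaction from a date not obtained, and the table puts them together again.

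Three stronger readings are tempting but not supported:

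- **Both duration tables drop the subject.** This is established only for Duration (Days). For Total Days the text is silent on what happens to the subject's total.
- **The minimum durations by onset day hold for both tables.** They do not, as Step 4 shows.
- **The primary safety results are biased.** They are not. Presence and maximum severity of a reaction do not use the end date.

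**Conclusion.** The point holds for Duration (Days), for local reactions and, through SAP 6.1.1.2, for systemic events. A reaction known to have lasted at least 16 days (adults) or 23 days (6 to <18 years) is treated as having no duration information. The bounds follow from the documents alone, given a Visit 2 within its window. The size of the effect on the mean does not: it depends on the assumed known mean and on how many reactions are continuing. The downward direction requires only that the known mean be below L. For Total Days, the supported conclusion is that the handling is unspecified and that both possible readings understate duration. This is an optional, low-priority improvement to supportive tables.

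**What to change.** Amend SAP 6.1.1.1, and carry the change to systemic events:

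1. Count reactions confirmed as continuing at Visit 2 separately from durations unknown because no date was obtained. List them as censored at Visit 2, with their minimum duration.
2. Show the maximum as ≥x days when a censored value exceeds the largest observed duration.
3. State that the mean, SD and range use reporters with a known duration, and print that number.
4. State that a Total Days value without an end date is handled the same way, using the minimum in Step 4.
5. Clarify the resolution rule. It now opens with a test on length ("Resolution is the last day on which the reaction is recorded in the e-diary if the reaction lasted 7 days"), while the Total Days rule tests whether the reaction went past the end of the diary period. Protocol 6.1 and 7.2.1.1 collect stop dates for symptoms ongoing on the last day the e-diary was completed. The SAP should use the CRF stop date for any such reaction, and otherwise the last e-diary day with the reaction. A plain cut at Day 7 or 14 would not do: if the diary was last completed on Day 4 with the reaction ongoing and the CRF stop date is Day 6, it would return Day 4.

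The cost is a few sentences in the SAP, one footnote and a short listing, all from data the protocol already collects. The downside is slightly more table work and possibly less favourable duration figures.

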### **Analysis Specifications**

The number of subjects reporting the specified reaction, mean, range (minimum, maximum), and standard deviation will be calculated from the number of subjects reporting the specified reaction.

The total days will be calculated as the sum total of reported days of the specified reaction. However, if the reaction continues beyond Day 7 or 14, the calculation of total days will include all days from the last e-diary day until the date of resolution collected on the CRF. If there is no known date when the reaction ended, then duration beyond Day 7 or 14 will be missing (unknown). Subjects with no reported reaction have no duration because it is not applicable.

➤ Summary of Day of Onset of Local Reactions

The number of subjects reporting the specified reaction or any reaction, mean, range (minimum, maximum), and standard deviation.

### **Analysis Specifications**

For the onset day of the specified reaction, if subjects report change in severity of the local reaction, only the first day of reporting that specific local reaction will be counted.

For the onset day of any local reaction, the first day of reporting any severity of any local reaction will be counted.

**Figures:**

A bar graph showing the percent incidence for the specified reaction and for any reaction, by day. These summaries will be compiled for each age category in addition to each age group.

**6.1.1.2. Systemic Events**

Note: Systemic events include fever, fatigue, headache, vomiting, diarrhea, muscle pain, and joint pain. Fever is discussed further in [Section 6.1.1.3](#). Use of antipyretic/pain medication is discussed in [Section 6.1.1.4](#).

**Endpoints:** Number and proportion of subjects reporting systemic events (fever, fatigue, headache, vomiting, diarrhea, muscle pain, joint pain) and severity of the systemic events.

- Analysis time points: The 7-day period (6- to <18-year age group) and 14-day period (18- to <65-year age group) following study vaccination.
- Analysis population: Safety population (additional handling is the same as that for local reactions in [Section 6.1.1.1](#)).

For each systemic event, severity will be derived by the maximum severity grade of the event based on the severity grading scale in Table 7.

**Table 7. Systemic Event Grading Scale (for All Age Groups and Categories)**

	GRADE 1 mild	GRADE 2 moderate	GRADE 3a severe	GRADE 4b
Fatigue (tiredness)	Does not interfere with activity	Some interference with activity	Prevents daily routine activity	Emergency room visit or hospitalization
Headache	Does not interfere with activity	Some interference with activity	Prevents daily routine activity	Emergency room visit or hospitalization
Vomiting	1 to 2 times in 24 hours	>2 times in 24 hours	Requires intravenous hydration	Emergency room visit or hospitalization
Diarrhea	2 to 3 loose stools in 24 hours	4 to 5 loose stools in 24 hours	6 or more loose stools in 24 hours	Emergency room visit or hospitalization
Muscle pain	Does not interfere with activity	Some interference with activity	Prevents daily routine activity	Emergency room visit or hospitalization
Joint pain	Does not interfere with activity	Some interference with activity	Prevents daily routine activity	Emergency room visit or hospitalization

Abbreviation: CRF = case report form.

- a. When subjects experience severe systemic events, the subject/legally acceptable representative/parent/legal guardian will telephone the study site. In the event that the subject/legally acceptable representative/parent/legal guardian does not call, the investigator will call the subject/legally acceptable representative/parent/legal guardian.
- b. Grade 4 assessment for systemic events should be made by the investigator and recorded as an AE on the CRF.

**Reporting Summaries:**

For each systemic event, the below summary tables will be generated following the same rules as for local reactions in [Section 6.1.1.1](#), where applicable:

- Summary of Subjects Reporting Systemic Events by Maximum Severity Grade of the Events
- Subjects Reporting the Specific Event or Any Systemic Event on Each Day
- Duration (Days) of Systemic Events
- Duration (Total Days) of Systemic Events
- Summary of Day of Onset of Systemic Events

**6.1.1.3. Fever**

Analysis time points and the analysis population will be the same as for systemic events in [Section 6.1.1.2](#).

090177e190dcce77Approved\Approved On: 06-May-2019 11:24 (GMT)

Axillary temperature will be measured and recorded to 1 decimal place and then grouped into ranges for the analysis according to Table 8 below. Fever is defined as an axillary temperature of  $\geq 37.5^{\circ}\text{C}$ .

**Table 8. Scale for Fever**

37.5 to 38.4°C
38.5 to 38.9°C
39.0 to 40.0°C
>40.0°C

**Reporting Summaries:**

For fever, summaries will be included in tables for systemic events following the same rules as for local reactions in [Section 6.1.1.1](#), where applicable.

**6.1.1.4. Use of Antipyretic/Pain Medication**

Analysis time points and the analysis population will be the same as for systemic events in [Section 6.1.1.2](#).

**Reporting Summaries:**

For use of antipyretic and/or pain medication, summaries will be included in tables for systemic events following the same rules as for local reactions in [Section 6.1.1.1](#), where applicable.

**6.1.1.5. Adverse Events**

**Endpoints:** Number and proportion of subjects reporting AEs and SAEs categorized according to MedDRA.

- Analysis time points: From the time of informed consent through and including Visit 2
- Analysis population: Safety Population
- Subgroups: For all ages and each age group (6 to <18 years old and 18 to <65 years old)

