6.1. Visit 1 - Vaccination (Day 1)

- Obtain written informed consent and, if applicable, assent (age dependent on local requirement) before performing any study-specific procedures.
- Obtain a subject number from IWR.
- Obtain and record the subject demography including date of birth, sex, race, and ethnicity.
- Obtain and record medical history and current medical conditions, including the presence of chronic conditions, medical history of significance such as cardiac, pulmonary, renal, hepatic, hematologic, neurological, and/or endocrinologic medical history, relevant surgical procedures and/or allergies (drug or nondrug), and their start and stop dates.
- Obtain and record vaccination history within 6 months before the study participation as described in Section 5.7. For diphtheria vaccine, obtain and record the date of last booster vaccination (the date may be beyond 6 months before study participation).
- Obtain and record any immunosuppressive drugs, including systemic corticosteroids, immune-modifying drugs, or monoclonal antibodies, received within 6 months before the study participation as described in Section 5.7.
- Assess and record smoking status as either smoker, ex-smoker, or never smoked during the 6 months prior to the study participation.
- Perform a physical examination evaluating any clinically significant abnormalities within the following body systems: general appearance, skin, head, eyes, ears, nose, throat, heart, lungs, abdomen, musculoskeletal, neurological, and lymph nodes, including worsening of medical history conditions. Record findings of physical examination on the physical examination record and, if appropriate, on the medical history CRF. If the condition started after informed consent was given, the condition should be recorded on the AE CRF.
- Perform a urine pregnancy test on female subjects of childbearing potential. A negative pregnancy test result is required before female subjects of childbearing potential may receive the investigational product.
- On the day of investigational product administration, measure the subject's axillary temperature (°C) using the digital thermometer prior to investigational product administration and record the temperature on the vital signs CRF. When multiple measurements are taken for the same time point, the most out-of-range (eg, highest) value must be reported.

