- Ensure that all of the inclusion criteria, none of the exclusion criteria, and none of the criteria for temporarily delaying vaccine administration are met. If a subject meets any

delay criteria for vaccination, all study procedures including the blood draw at Day 1 should be delayed until the day of vaccination.

- After all eligibility criteria are confirmed, obtain the investigational product assignment from IWR. Refer to the SRM for further instructions and requirements for recording screen failure subjects.
- Prior to vaccination, collect a blood sample (approximately 10 mL) for immunogenicity assessments and record sample tracking information on the CRF.
- Administer a single 0.5-mL injection of the investigational product into the deltoid muscle of the nondominant arm, unless medically contraindicated, in which case the injection may be administered in the dominant arm.
- Observe the subject for at least 30 minutes after the investigational product administration for any acute reactions. Record any AEs in the subject's source documents and on the AE CRFs.
- Provide training in the use of the e-diary device.
 - For subjects aged 6 to <18 years:
 - Train the subject's legally acceptable representative/parent/legal guardian to use the e-diary and set up the e-diary for the subject. Specific instructions for the site user and the subject's legally acceptable representative/parent/legal guardian to use the e-diary will be provided under separate cover.
 - Issue an e-diary, measuring device (caliper [range: 1 to 14+ for subjects aged 6 to <12 years or caliper [range: 1 to 21+] for subjects aged 12 to <18 years), and digital thermometer and provide instructions for usage.
 - Ask the subject's legally acceptable representative/parent/legal guardian to complete the e-diary from Days 1 to 7 after investigational product administration, where Day 1 is the day of investigational product administration.
 - Ask the subject's legally acceptable representative/parent/legal guardian to contact the investigator immediately if the subject experiences a severe local reaction (redness or swelling) at the injection site measuring >14 caliper units (greater than 7 cm) for subjects aged 6 to <12 years or >20 caliper units (greater than 10 cm) for subjects aged 12 to <18 years to arrange an unscheduled visit as specified in Section 6.3.

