8.1.4. Time Period for Collecting AE/SAE Information

The time period for actively eliciting and collecting AEs and SAEs (“active collection period”) for each subject begins from the time the subject/legally acceptable representative/parent/legal guardian provides informed consent, which is obtained before the subject’s participation in the study (ie, before undergoing any study-related procedure and/or receiving investigational product), through and including Visit 2.

For subjects who are screen failures, the active collection period ends when screen failure status is determined.

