### 4.1. Safety Analysis Set

The safety population will include all subjects who receive 1 dose of study vaccine. The safety population will be the only analysis population for the primary endpoints.

For local reactions, systemic events, fever, and use of antipyretic/pain medication, the definition of the denominators for the percentage calculations will be described in [Section 6.1.1.1](#) based on electronic diary (e-diary) record. In addition, these tables will be generated without e-diary data that have been confirmed by the subject to have been entered in error. Data-entry errors will be discussed in the clinical study report text and documented in a separate listing.

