##### 6.1.1.1. Local Reactions

**Endpoints:** Number and proportion of subjects reporting local reactions (redness, swelling, pain at injection site) and severity of the local reactions.

- Analysis time points: The 7-day period (6- to <18-year age group) and 14-day period (18- to <65-year age group) following study vaccination.
- Analysis population: Safety population (Definitions of denominators for the summary tables are described in each reporting summary section).
- Subgroups: Each age group (6 to <18 years old and 18 to <65 years old) and each age category (6 to <12 years old, 12 to <18 years old, 18 to <50 years old, and 50 to <65 years old) in each age group.

For each local reaction, severity will be derived by the maximum severity grade of the reaction based on the severity grading scale of the local reactions in Table 3 for subjects aged 6 to <12 years, and Table 4 for subjects aged 12 to <18 years and those aged 18 to <65 years.

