**Reporting Summaries:**

➤ Adverse Events Reported After Study Vaccination

The sample size, number and percentage of subjects reporting at least 1 event of each preferred term, arranged by system organ class with the associated Clopper-Pearson 95% CI, and number of occurrences of the event.

090177e190dcce77\Approved\Approved On: 06-May-2019 11:24 (GMT)

The below summary tables will be generated in the same way as the summary above. For death, only number and percentage of subjects reporting death will be summarized:

- Related Adverse Events Reported After Study Vaccination
- Serious Adverse Events Reported After Study Vaccination
- Related Serious Adverse Events Reported After Study Vaccination
- Severe Adverse Events Reported After Study Vaccination
- Related Severe Adverse Events Reported After Study Vaccination
- Life-Threatening Adverse Events Reported After Study Vaccination
- Related Life-Threatening Adverse Events Reported After Study Vaccination
- Adverse Events Leading to Discontinuation Reported After Vaccination
- Related Adverse Events Leading to Discontinuation Reported After Vaccination
- Immediate Adverse Events Reported After Vaccination (Immediate adverse events stand for events occurred during 30-minutes postvaccination observation)
- Related Immediate Adverse Events Reported After Vaccination
- Deaths During the Study Period
- Related Deaths During the Study Period

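### Does the SAP leave open whether adverse events that start before vaccination count in the tables titled as after vaccination?

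*SAP*

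**What the plan says.** SAP 6.1.1.5 (Adverse Events) sets the AE analysis time points as "From the time of informed consent through and including Visit 2". The population is the safety population, defined in SAP 4.1: "The safety population will include all subjects who receive 1 dose of study vaccine".

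The reporting summaries in the same section list 14 tables. The first is titled "Adverse Events Reported After Study Vaccination" and counts "subjects reporting at least 1 event of each preferred term, arranged by system organ class with the associated Clopper-Pearson 95% CI". Eleven more carry an after-vaccination title. The remaining two, on deaths, are titled by the study period instead. The only timing definition attached to any AE table is the 30-minute one for immediate events.

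In the protocol, section 8.1.4 states that active AE collection "begins from the time the subject/legally acceptable representative/parent/legal guardian provides informed consent". In section 6.1, the first instruction for Visit 1 reads "Obtain written informed consent and, if applicable, assent (age dependent on local requirement) before performing any study-specific procedures", and a later one reads "Prior to vaccination, collect a blood sample (approximately 10 mL) for immunogenicity assessments". The same section tells sites to record on the AE form any condition found at examination that began after consent.

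**The concern.** The stated window and the table titles do not match, and no onset rule joins them. SAP 5.3 covers missing data for immunogenicity, local reactions and systemic events but not AE dates. Protocol 9.4 gives no start point for AEs, and the primary AE endpoint gives only an end, Visit 2. For local reactions the same SAP field is explicit: "Analysis time points: The 7-day period (6- to <18-year age group) and 14-day period (18- to <65-year age group) following study vaccination".

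The interval between consent and injection exists for every subject, and it contains a blood draw. A faint or bruise at that draw would have a Day 1 onset date, as would the same event after the injection. Protocol 8.1.5 asks for causality to study procedures only for serious events, so that field would not separate the two.

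At stake is a primary endpoint in a study without a control arm. If a programmer followed the window rather than the titles, an event that preceded the vaccine would appear in a table saying it followed.

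**Working it through.** **Step 1: the texts side by side.**

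| Item | Start | End |
|---|---|---|
| Active AE collection (Protocol 8.1.4) | Consent | Visit 2 |
| AE analysis time points (SAP 6.1.1.5) | Consent | Visit 2 |
| Titles of 12 AE tables (SAP 6.1.1.5) | Vaccination | Not stated |
| Titles of 2 death tables (SAP 6.1.1.5) | Study period | Study period |

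The SAP window repeats the collection period. The titles then narrow 12 tables. A wide data window with narrower tables is not a contradiction.

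**Step 2: which tables could be affected.** The 14 tables are 7 restricted to related events, plus deaths, immediate events, discontinuations, and four others: all, serious, severe and life-threatening.

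- Related tables: an event before the injection cannot be attributed to the vaccine, and Protocol 8.1.5 requires a causality assessment for every AE.
- Immediate events: the 30-minute definition fixes the timing.
- Deaths and discontinuations: the safety population holds only vaccinated subjects, so a death before vaccination is impossible there, and a pre-vaccination event that leads to discontinuation is very unlikely.
- Serious and life-threatening events: the subject would have to have the event after consent and still be vaccinated. Protocol 4.2 (exclusion 2), Protocol 4.3 (acute illness) and the eligibility check before product assignment in Protocol 6.1 make this remote.

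That leaves the all-AE table and, marginally, the severe one.

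**Step 3: effect on the overall AE proportion.** Let q be the share of subjects with a pre-vaccination event, p the true post-vaccination AE proportion, and N = 200 (Protocol 3.3). If the two are independent, the extra subjects number N × q × (1 − p), which cannot exceed N × q. The documents give neither q nor p. I assume q = 0.1%, 0.5% and 1%, and p = 20% for illustration.

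| q | Bound N × q | Extra at p = 20% | Proportion 1 − (1 − p)(1 − q) |
|---|---|---|---|
| 0.1% | 0.2 | 0.16 | 20.1% |
| 0.5% | 1.0 | 0.80 | 20.4% |
| 1% | 2.0 | 1.60 | 20.8% |

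The exact 95% CI for 40/200 is 14.7% to 26.2%, so each shift is small against the sampling error. The bound in the second column does not depend on p.

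**Step 4: effect on one preferred-term row.** Take a term with no post-vaccination case and add one event. Clopper-Pearson limits, from beta quantiles:

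| N | No event | One event |
|---|---|---|
| 200 | 0% (0 to 1.83%) | 0.5% (0.01 to 2.75%) |
| 150 | 0% (0 to 2.43%) | 0.67% (0.02 to 3.66%) |
| 50 | 0% (0 to 7.11%) | 2.0% (0.05 to 10.65%) |

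**Step 5: how often.** Protocol Table 6 uses 1 − (1 − rate)^N. At 1.0% and N = 200 this gives 0.866, matching the stated 0.87. With q in place of the rate, the chance of at least one pre-vaccination event of any kind among 200 subjects is 18%, 63% and 87% for the three values of q. These apply to the table as a whole and not to a given row. If q were spread evenly over five terms (illustrative), a given row would have 1 − 0.999^200 = 18% at q = 0.5% and 1 − 0.998^200 = 33% at q = 1%.

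**The case for a change.** The strongest case for a change is that a title is not a derivation rule. The only explicit timing statement for AEs is the consent-to-Visit-2 window, and a programmer who applied it literally would count pre-vaccination events. The titles also speak of reporting rather than onset. Neither reading says what to do with a Day 1 event whose order is unknown, or where excluded events would be shown. One sentence would settle this, and SAP version 2.0 already amended this section for omissions.

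Part of this stands: no onset rule is written down, and the documents do not show whether the AE form captures onset time. The rest is weaker. The death tables have their own wording, which gives modest support to reading the other titles as a deliberate restriction. The contrast with local reactions proves little, because those come from a diary that starts on the day of vaccination and could have no earlier window. Sites must already place some Day 1 events relative to the injection, since Protocol 7.2 has reactions within 30 minutes recorded and the SAP tabulates immediate events. The interval is also normally short: the schedule of activities puts consent on Day 1, and under Protocol 4.3 a delay moves the study procedures to the vaccination day. A gap of several days can only be inferred, and nothing in the documents gives its length or frequency.

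**Conclusion.** The observation about the text is right, but no change follows. The SAP states the collection window and lets the table titles carry the restriction to post-vaccination events. An analyst following the plan in the ordinary way would reach sound tables, and an added sentence would only write down a rule that the titles already imply.

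Even under the literal reading, the overall AE count would gain at most 0.2 to 2.0 of 200 subjects, and a preferred-term row would typically change by about one event. These sizes rest on assumed pre-vaccination event shares of 0.1% to 1%; the 20% AE proportion is only illustrative. All analyses are descriptive and no hypothesis is tested (Protocol 9.1, SAP 5.1), so no conclusion of the study would turn on such an event.
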